12 QUALITY MANAGEMENT

12.1 Independent Scientific Committee

The Independent Scientific Committee (ISC) is composed of independent external experts (from organisations or institutions which are not partners of id.DRIVE) with good expertise/experience relevant for id.DRIVE studies on infectious diseases, vaccines, related preventive measures and therapeutics for infectious diseases in Europe.

The roles and responsibilities of the ISC are the following:

- reviews and makes recommendations for study documents (protocols and SAPs),
- reviews and makes recommendations for study reports, and
- reviews and formulates recommendations for the master scientific documents, which are codeveloped by the id.DRIVE partners to harmonise study methodology (e.g., protocols and analyses to assess severe RSV, long-term effectiveness, RSV infection, or transmission).

12.2 Quality Assurance and Audit Committee

The Quality Assurance and Audit Committee (QAAC) of id.DRIVE composed of one quality assurance expert of each Pharmaceutical Company Partner and one quality assurance expert of the Co-Coordinators. The QAAC's mission is to provide, at the partnership level, guidance on implementation, conduct, monitoring and quality assurance of the Studies, as well as to ensure that data quality is in line with the Study request and to, when necessary and to the extent possible, identify areas for improvement.

The QAAC seeks to develop and sustain a reasonable and feasible mechanism to support quality management together with P95 as the Study Sponsor of the Studies.

The QAAC provides quality management recommendations for Study Contributors and oversees any audit at the Study Contributor level if needed; the audit is subcontracted to an external qualified consultants' auditor.

12.3 Monitoring

Monitoring activities include:

- Before study start, the Study Contributor will be asked to complete a quality management questionnaire to inform the Study Team on all aspects of the study conduct.
- Before study start, an SIV will be organised by the Study Team.
- During study conduct, regular Study Contributor contacts will be organised to monitor study progress (number of cases and controls enrolled), to ensure regular data input to the id.DRIVE

EDC system and to discuss potential protocol deviations or other issues related to the study conduct.

- Study Contributors will be asked to keep high-level Screening Logs (including number of modified SARI patients missed or not consented for the study with age group and gender), as they may affect interpretation of trend data.
- Monitoring shall occur as described in the id.DRIVE Monitoring Plan.

The Study Contributor investigators must permit any external auditor mandated by the QAAC of the id.DRIVE partnership or the Study Requestor, the IEC, auditors and representatives from regulatory authorities direct access to all study-related documents. Participant confidentiality will be protected at all times.

12.4 Data quality checks at central level

Programmed checks are run on Castor[®]-extracted data and the identified data issues are manually queried in Castor[®] every two weeks. After the Study Contributor responds to the queries by updating or confirming the data entered in Castor[®], P95 Epidemiology & Pharmacovigilance closes the queries. Per agreement, the identified data issues are also sent in an MS Excel document to the corresponding Study Contributors. All the queries should be closed before database lock.

13 LIMITATIONS OF THE RESEARCH METHODS

- Due to high demand and limited vaccine supplies, European countries often prioritise highrisk groups such as the elderly, residents in care facilities, and those with specific chronic conditions. This prioritisation creates potential confounding factors in studies on VE. Untangling waning of vaccine-induced immunity, varying VE against different RSV subtypes, and infection-acquired immunity is challenging due to the complex interaction of these factors.
- Infection-acquired immunity protects against re-infection but may wane and act as an effect modifier of VE. Hybrid immunity, combining infection-acquired and vaccine-induced immunity, is suggested for optimal protection against severe disease. However, identifying past RSV infection poses challenges due to potential underreporting or misclassification, especially with clinical-based diagnoses and the absence of serological results. This prior infection status could also introduce confounding, influencing vaccination decisions.
- The TNCC study design minimises unmeasured confounding tied to general health careseeking behaviour [24]. However, specific health practices may still confound results. Vaccination uptake may be higher among individuals strongly adhering to preventive practices such as social distancing, reducing natural infection risk. Conversely, being vaccinated may lead to a false sense of security, relaxing precautions and increasing exposure risk. Additionally, those likely to get vaccinated against RSV may also favour influenza, SARS-CoV-2, and/or pneumococcal vaccinations, potentially biasing results. Sensitivity analyses redefining control groups will explore this bias. In this study, exposure ascertainment is based on multiple sources including vaccine registries, vaccination cards and medical records. Although vaccination status captured in medical records is neither validated against primary records nor validated verbally with the patient, misclassification was likely limited: complete exposure data was required for a participant to be retained in the id.DRIVE study (mandatory variables included date of administration, dose number and vaccine brand).
- In Germany there is no vaccine registry available, and paper vaccination cards are used for documentation. In some cases, the vaccination card may not be available as a physical document at the time of hospital admission, thus, provision of the vaccination data card may be foreseen by relatives, which can be challenging. In addition, there is a chance of incomplete data because of unreadable handwriting on vaccination cards. Therefore, misclassification of vaccination status may be greater for data collected in German sites.
- The PROMISE generic RSV VE protocol recommends the exclusion of persons with a contraindication to the RSV vaccine being studied, in order to only capture the eligible population. Such patients are not excluded from the present study, as vaccine contraindications cannot be collected. However, numbers are expected to be small.
- Despite RT-PCR's high specificity and sensitivity, diagnostic inaccuracies pose potential bias, influenced by factors like sampling technique, specimen type, number of specimens [17, 18], and timing. In RSV RT-PCR, declining sensitivity over time may yield more false negatives among vaccinated, overestimating VE. Sensitivity analyses, such as varying time between symptom onset and sampling, as well as addition of pre-admission rapid antigen testing, will

explore potential misclassification bias. Study staff follow guidance for proper specimen collection, ensuring a robust testing procedure.

- Unaccounted potential confounders in this study, such as ethnicity and socio-economic status, could lead to overestimated VE when certain groups are less likely to be vaccinated. TNCC studies, limited to those accessing healthcare or hospitalised, may not generalise to disadvantaged groups with poor access or nursing home residents, affecting result applicability.
- This study does not measure frailty, an important potential effect modifier of VE. Frailty has been shown to affect immune responses in older adults to vaccines for infections such as influenza, shingles and pneumococcus [19]. Frailty, impacting immune responses in older adults, lacks a consensus definition and measurement method. Given the study's focus on the general population and frailty's complexity, we collect information on related variables like age, body mass index (BMI), long-term care residence, and chronic conditions instead of directly measuring frailty.
- Last, estimating sample sizes for brand-specific VE is challenging due to unpredictable and evolving attack rates and vaccination coverage. This challenge is exacerbated by the increasing fragmentation of the vaccine market with more available RSV vaccination products. Despite our study's extensive European hospital network, obtaining sufficient samples for accurate estimates of primary and secondary objectives may be challenging.

14 ETHICAL AND REGULATORY CONSIDERATIONS, RETENTION OF DATA AND OF BIOLOGICAL SAMPLES

14.1 Guiding principles

To ensure the quality and integrity of research, this study will be conducted under the International Ethical Guidelines on Epidemiological Studies issued by the Council for International Organisations of Medical Sciences (CIOMS) [20], Good Epidemiological Practice (GEP) [21], the ethical principles that have their origins in the Declaration of Helsinki, and any applicable national laws, regulations and guidelines.

This is an observational study. Therefore, there is no direct benefit to the participants. Nevertheless, there are important potential societal benefits derived from this VE study. Close monitoring of the effectiveness of RSV vaccination products is essential to guide decision-making regarding vaccination products marketing approval, optimisation of vaccination programmes and future RSV vaccine development.

14.2 Ethics approval

The Study Contributor-specific protocols will be submitted to relevant IECs following local regulations and the declaration of Helsinki. Copies of the appropriate IEC approvals will be collected from each Study Contributor and archived according to the local regulations, but at least for 10 years. The only exception is where the study is part of an ongoing routine programme evaluation required by a ministry of health or a requisite part of the public health institution's work and would therefore fall outside the mandate for IECs. In these cases, a statement that no formal approval from an IEC is required is sufficient.

14.3 Informed consent

Written informed consent will be obtained from all participants/guardians as specified by the national/regional IEC, if applicable. The following information should be specified in the informed consent form (ICF) which will be translated in local language: who is responsible for the study, aim of the study, risk of study procedures nature of processed data, purposes of processing, purpose of the use of the data including potential future use of the data to advance knowledge on vaccines, recipients of possible data transfers, rights of the study participants, and consequences of not accepting the informed consent. Specific consent procedures may be needed for patients in poor health conditions (e.g., oral witnessed consent, consent by next of kin). If informed consent will not be required, the reason will be stated.

14.4 Independent ethics committee/Institutional review board

Consistent with local regulations and prior to enrolment of participants at a given Study Contributor, the study protocol together with its associated documents (e.g., ICF) will be submitted by the Study Contributor to the responsible institutional review board (IRB)/IEC for its review. Participant enrolment will not start before the Study Contributor has obtained written confirmation of a favourable opinion/approval from the relevant central or local IRB/IEC. The Study Contributor will promptly and before first participant enrolment inform the Study Team that ethical approval has been granted. The IRB/IEC will be asked to provide documentation of the date of the meeting at which the favourable opinion/approval was given that clearly identifies the study, the protocol version, and the ICF version reviewed.

Before implementation of any substantial changes to the protocol, protocol amendments will also be submitted to the relevant IRB/IEC in a manner consistent with local regulations. It is the responsibility of the Study Contributor (local) investigator to have prospective approval of the study protocol, protocol amendments, and ICFs, and other relevant documents, if applicable, from their local IRB/IEC and provide documentation of approval to the Study Team.

Should the study be terminated early for any unanticipated reason, the Study Contributor (local) investigator will be responsible for informing the IRB/IEC of the early termination.

14.5 Participant's confidentiality

Data will be pseudonymised at the Study Contributor level prior to data transfer to P95 Epidemiology & Pharmacovigilance. All parties will ensure protection of participants' personal data and will not include participant names on any study forms, reports, publications, or in any other disclosures, except where required by law. In accordance with local regulations in each of the countries, participants will be informed about data handling procedures and asked for their consent. Data protection and privacy regulations will be observed in capturing, forwarding, processing, and storing participant data. Every effort will be made to protect participant confidentiality according to Regulation (EU) 2016/679 of the European Parliament and of the Council of 27 April 2016 on the protection of natural persons regarding the processing of personal data and on the free movement of such data, and repealing Directive 95/46/EC (GDPR).

14.6 Changes to the protocol

Changes to the protocol will be documented in written protocol amendments. Such protocol changes will be discussed and agreed upon with the Study Team prior to their implementation. Major (i.e., substantial, significant) amendments will usually require submission to the relevant IRB/IEC for approval or favourable opinion and to the relevant regulatory authorities, if applicable. In such cases, the amendment will be implemented only after approval or favourable opinion has been obtained.

Minor (non-substantial) protocol amendments, including administrative changes, will be filed at each participating Study Contributor and will be submitted to the relevant IRB/IEC or regulatory authorities where required by pertinent regulations.

Confidential

id.DRIVE Study Contributor Master Protocol for respiratory syncytial virus vaccine effectiveness study

14.7 Secondary data use

The data generated as part of this study may be used for future research related to the expansion of the knowledge, prevention and control of infectious diseases. For this secondary data use, id.DRIVE governance principles will be respected as detailed in the id.DRIVE Governance Charter. The Governance Charter can be made available by the Co-Coordinators upon written request.

15 STUDY MANAGEMENT AND LOGISTICAL ASPECTS

This study will be performed by the Study Contributor investigator(s), with guidance, input, review, and approval of the Study Team, including development of materials, recruitment, training, management of network study sites (Study Contributors), EDC, data management and analysis.

The Study Contributor investigator(s) and all study staff will conduct the study in compliance with the final version of this protocol. The rights, safety and well-being of the participants are the most important considerations and prevail over the interests of science and society. All personnel involved in the conduct of this study must be qualified by education, training, and experience to perform their tasks.

15.1 Training

Study Contributor investigators and data collectors will be trained on the study protocol before the start of the study. They will receive the protocol and study training material.

15.2 Data capture

The data will be collected using an EDC system as described in the DMP.

15.3 Retention

To enable evaluations and/or audits from regulatory authorities or others, the Study Contributor investigator(s) agree(s) to keep documents and data relating to the study in an orderly manner in a secure study file, which will be available for audits/inspections, for a period of at least 10 years after the end of the study or longer according to local requirements and legislation. Documents to be archived include the participant enrolment log and the signed ICFs. In the event that archiving of the file is no longer possible at the Study Contributor, the Study Contributor/investigator will be instructed to notify the Study Team. The Study Contributor investigator must contact the Sponsor before destroying any study-related documentation. It is the responsibility of the Sponsor to inform the Study Contributor of when these documents no longer need to be retained.

Biological specimens might be collected for future research. Retention, storage, and access rights will be predefined and described as appropriate.

15.4 Discontinuation of study participation/Withdrawal from the study

Participation in the study is strictly voluntary. A participant has the right to withdraw from the study at any time and for any reason, without any negative impact on the quality of care or on the relationship with the treating doctor(s). All attempts should be made to determine the underlying reason for the discontinuation/withdrawal and, if possible, the primary underlying reason should be recorded. Data collected up to the time of consent withdrawal will be considered for the analysis.

15.5 Study termination

The Study Team reserves the right to terminate the study at a specific Study Contributor at any time. Reasons for terminating the study include but are not limited to the following:

- The Study Contributor does not respond to study management requests.
- Repeated protocol deviations/poor protocol compliance.

16 REPORTING AND DISSEMINATION OF RESULTS

16.1 Study protocol

The study protocol and final study report will be included in the HMA/EMA catalogue of real-world data studies.

16.2 Management and reporting of adverse events/adverse reactions

This is a non-interventional epidemiological study for assessing the effectiveness of recommended or routine RSV vaccination based on primary and secondary data collection. Treatments, vaccines, and pharmaceutical prevention will be collected as part of secondary data collection (registries and/or patient files). Therefore, no adverse events or adverse reactions are collected. The Study Contributors conducting the study should follow local requirements as regards the submission of cases of suspected adverse reactions to the competent authority in the country where the reaction occurred.

In case additional safety reporting is required for a specific Study Requestor, only serious adverse events (SAEs) related to the receipt of the investigational products, of which the Study Contributors become aware, will be reported to the Study Requestor. The individual case safety report (ICSR) form for reporting SAEs is provided in the Investigator Site Files (ISFs).

16.3 Progress, interim and final reports

Progress reports will be provided to the Study Requestors every two months since enrolment of the first study participant. Progress reports will provide an overview of the number of cases, number of controls, number of study participants immunised with any RSV vaccination product brand and number of study participants immunised with the RSV vaccination product brand of interest.

Interim analysis for a specific VE objective will be performed as soon as a prespecified number of cases required for the brand-specific VE estimates is reached. The progress reports will be used to monitor this required number of cases.

A final study report will be written for the RSV vaccine. The id.DRIVE ISC will review all study reports (interim and/or final, as applicable) and the written comments by the Study Requestor. The ISC will provide recommendations for the integration of the Study Requestor comments. The study report(s) (interim and/or final, as applicable) will be submitted to the EMA by the Study Requestor depending on regulatory requirements. This process is further described in the id.DRIVE Governance Charter.

16.4 Publication

Scientific publication(s) of the study results will be prepared. Co-authorship will be defined following the International Committee of Medical Journal Editors (ICMJE) criteria and the Good Publication Practice (GPP). All publications will be open-access.

Study Contributors are allowed to develop publications based on their raw patient-level data or cleaned pseudonymised patient-level data collected in the scope of the id.DRIVE Study following the id.DRIVE Governance Charter.

17 FUNDING

id.DRIVE is a public-private partnership funded by the Pharmaceutical Company Partners and leveraging health capacities from public partners and sites. This generic Master Protocol has been developed by the id.DRIVE partnership, which has received funds from AstraZeneca, Bavarian Nordic, CureVac, GlaxoSmithKline (GSK), Janssen, Moderna, Novavax, Pfizer, Sanofi, and Valneva, leveraging public health capacity from Fundación para el Fomento de la Investigación Sanitaria y Biomédica de la Comunitat Valenciana (FISABIO) and the Finnish institute for Health and Welfare (THL) and existing infrastructure at P95. Other Partners (Pharmaceutical Companies or other Institutions) may join the id.DRIVE partnership at later stages. Cost sharing principles are defined in the id.DRIVE Consortium governance charter. The execution of the brand-specific study will be further funded by [Study Requestor] requesting the specific study.

ANNEX 1: SAMPLE SIZE CALCULATIONS, TECHNICAL SPECIFICATIONS

Sample size calculation

The goal of the sample size calculations is to calculate the minimally required sample size that ensures desirable properties of the VE estimates. Examples of desirable properties are the expected length of the 95% CI, the expected lower half-width of the 95% CI or power to detect statistical significance of a pre-specified effect size. Two approaches to sample size calculations have been developed; analytical and simulation-based. While analytical methods do have the advantage of computational speed, simulation-based methods are sometimes developed to closer mimic the actual study design than proposed analytical approaches at the cost of requiring additional parameter assumptions.

Analytical approach: power and minimal detectable VE

The power is the likelihood of statistical significance when there is a true effect while the minimal detectable VE is the smallest VE that can be detected as significantly greater than zero in a given study using hypothesis testing. The power and minimal detectable VE can be derived from the 2x2 table of interest cross-tabulating the expected number of cases and controls with the expected number of subjects within the relevant exposure group and within the appropriate comparator group.

Particularly, to derived the power for case-control studies, first calculate

$$M = \left| \frac{(\lambda - 1)(P - 1)}{1 + (\lambda - 1)P} \right|,$$

and

$$p_c^* = \frac{P}{r+1} \left(\frac{r\lambda}{1+(\lambda-1)P} + 1 \right),$$

where λ is the relative risk, P is the exposure prevalence and r is the case-control ratio. Then, the power can be derived from

$$z_{\beta} = \frac{\frac{MP\sqrt{nr}}{\sqrt{r+1}} - z_{\alpha}\sqrt{(r+1)} p_{c}^{*}(1-p_{c}^{*})}{\sqrt{\frac{\lambda P(1-P)}{[1+(\lambda-1)P]^{2}}} + r P (1-P)},$$

where z_{α} and z_{β} are critical values for the standard normal distribution²⁰.

The minimal detectable VE for a case-control study is estimated as

$$VE_{MD} = 1 - RR_{MD(RR<1)},\tag{1}$$

²⁰ WOODWARD, M. (2013). *Epidemiology: Study Design and Data Analysis, 3rd Ed.*, Chapman and Hall/CRC.

where $RR_{MD(RR<1)}$ is the minimal detectable approximate relative risk (RR) in a case-control study, if RR < 1, or

$$RR_{MD(RR<1)} \cong 1 + \frac{-b - \sqrt{b^2 - 4a(r+1)}}{2a},$$
 (2)

where

$$a = r\gamma^2 - \frac{Nr\gamma(1-\gamma)}{\left(\frac{z_{\alpha}+z_{\beta}}{2}\right)^2(r+1)} \quad ; b = 1 + 2r\gamma,$$

for 'cases to controls' ratio r, coverage γ , total number of subjects N, and where z_{α} and z_{β} are the standard normal z-scores for the type I and type II error rates²⁰.

For case-control studies with multiple exposure categories (k > 2), 3 generic exposure categories exist: (1) the exposure group of interest, (2) the appropriate comparator group and (3) other exposure groups not relevant for the comparison, resulting in a $3x^2$ cross table. Starting from the assumptions on the case-control ratio and on the proportions of subjects belonging to each of the three exposure categories (derived from assumptions on brand-specific vaccination coverage, overall vaccination coverage and vaccination history), the relative cell frequencies of the $2x^2$ table of interest can be derived, based on which all parameters required for sample size calculations are derived.

Simulation-based approach

Data generation workflow

Notation

Before describing the data generation workflow, the following parameters which act as input for the model have to be defined:

- 1. $VE_{x,overall}$: the overall VE of exposure x, the corresponding odds ratio is $OR_{x,overall} = 1 - \frac{VE_{x,overall}}{100}$.
- 2. c = P(unexposed | control): proportion of unexposed subjects among the controls
- 3. $P_x = P(exposure \ x | exposed, control)$: brand share of exposure x among the exposed
- 4. *r*: ratio of cases to control (that is, number of cases per one control)

General set-up

In each simulation run, a dataset is constructed by combining data generated for a number of individual Study Contributors. We will denote the total number of Study Contributors as k and the total sample size as N. Additionally, it is assumed that each Study Contributor contributes the same number of subjects, i.e. $\frac{N}{k}$. In order to allow for variability in the underlying vaccine effects across Study Contributors, the VE can be different from Study Contributor to Study Contributor. In the next section, it is described how data for one Study Contributor is generated given the Study Contributor-specific VEs for all exposures. The subsequent section describes how the VE are varied across the Study Contributors to introduce between-Study Contributor variability.

Simulating data at the Study Contributor level

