For each simulated dataset, an estimate of the (r)VE and the corresponding 95% CI is obtained using one of the following procedures:

²¹ THOMPSON, M. G., STENEHJEM, E., GRANNIS, S., et al. (2021). Effectiveness of Covid-19 Vaccines in Ambulatory and Inpatient Care Settings. N Engl J Med, 385(15):1355-71. DOI: https://doi.org/10.1056/NEJMoa2110362.

Two-stage pooling / random-effects meta-analysis (RE-MA)

- The simulated dataset is restricted to represent the data of interest.
- The Study Contributor-specific expected OR on the log-scale of the (relative) treatment effect is calculated using a logistic regression model with the disease status as the outcome and the exposure status as a covariate.
- The Study Contributor-specific log OR estimates are combined using a random-effects metaanalysis (RE-MA) model. More particularly, the log OR estimates are combined using the Hartung-Knapp-Sidik-Jonkman estimator to obtain an estimate of the median overall log OR and the corresponding two-sided 95% CI.
- The pooled log OR and the corresponding CI are then back-transformed to obtain an estimate and 95% CI of the median overall VE.
- The overall VE estimate and the length of the CI are stored for each simulation.

Generalised estimation equations (GEE)

- The simulated dataset is restricted to represent the data of interest.
- The expected OR on the log-scale of the treatment effect is estimated using a logistic regression model with the disease status as the outcome and the exposure as a covariate. The estimates are obtained using the GEE method in which the Study Contributors are considered as clusters and the variances are calculated using a robust sandwich estimator.
- The estimated log OR and the corresponding CI are then back-transformed to obtain an estimate of the mean overall (r)VE and its 95% CI.
- The overall (r)VE estimate and the length of the CI are stored for each simulation.

Generalised linear model/generalised additive model (GLM/GAM)

- The simulated dataset is restricted to represent the data of interest.
- The expected OR on the log-scale of the treatment effect is estimated using a logistic regression model with the disease status as the outcome and the exposure as a covariate.
- The estimates are obtained using the GLM/GAM method in which the Study Contributors are considered as fixed effects.
- The estimated log OR and the corresponding CI are then back-transformed to obtain an estimate of the mean overall (r)VE and its 95% CI.

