- The overall (r)VE estimate and the length of the CI are stored for each simulation.

Number of simulations performed

For each combination of parameter settings, a total of 500 simulations are recommended. On empirical basis, this number of simulation runs leads to stable Monte Carlo CIs while limiting the computational burden.

Summary measures of the simulation study

For each combination of the study characteristics, the measure of interest is obtained from the 500 simulations, e.g.

- The expected range of the 95% CI is defined as the mean range of the CI obtained from the 500 simulations.
- The expected lower half width of the 95% CI is defined as the mean lower half width of the CI obtained from the 500 simulations.
- The expected power to detect a VE significantly different from 0 is defined as the proportion of the CIs that do not include 0.

For each measure, 95% Monte Carlo CIs were constructed based on the respective Monte Carlo standard errors observed in the simulations.

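### With several controls per case and coverage of about 10–30%, the Annex 1 minimal-detectable-VE approximation overstates power relative to the Annex's own power formula, even after its printed root sign and z term are corrected

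*Protocol*

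**What the plan says.** Under the heading on the analytical approach, Annex 1 says that power and minimal detectable VE both come from the same 2x2 table of cases and controls by exposure. It defines the second quantity thus: "the minimal detectable VE is the smallest VE that can be detected as significantly greater than zero in a given study using hypothesis testing".

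For power, the Annex formula is written in λ and P ("where λ is the relative risk, P is the exposure prevalence"), and for the third input it says only that "r is the case-control ratio". Its z_α term carries the pooled exposure proportion p_c*. Its denominator carries the variance under the alternative.

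Equation 2 then gives, as a quadratic root with coefficients a and b, the quantity that "is the minimal detectable approximate relative risk (RR) in a case-control study, if RR < 1". It is written "for 'cases to controls' ratio r", coverage γ and total N. Its z values are described as "standard normal z-scores for the type I and type II error rates". The RR is labelled approximate, and no range of validity is given.

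No level, power target, N, r, coverage or VE is fixed. Section 11.10 leaves sample sizes to each Study Requestor-specific protocol. The Annex also offers a simulation route, in which "The expected power to detect a VE significantly different from 0 is defined as the proportion of the CIs that do not include 0".

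**The concern.** Two analytic tools for the same table should give nearly the same answer: the VE that equation 2 calls detectable at a target power should have about that power in the power formula. If it does not, a requestor-specific protocol could state a VE as detectable with 80% power when the design has clearly less, or could read off too small an N.

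This Annex is the common source for every brand-specific calculation. Section 11.10 says that all cases and controls are recruited, so r is not set by design and can fall well below 1. Section 13 warns of a fragmenting vaccine market, so low brand coverage is plausible as well.

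**Working it through.** **Inputs.** Two-sided 5% (z_α = 1.960) is an assumption; the Annex's meta-analysis procedure uses a "median overall log OR and the corresponding two-sided 95% CI", but the analytic part fixes no sidedness. Power of 80% (z_β = 0.842) is also an assumption. N, r (cases per control) and coverage are varied because the protocol gives none. The radicals in the power formula are taken over the whole variance terms. There is no stated figure to reproduce, so the two formulas are compared with each other.

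**Step 1: correcting equation 2.** For realistic N, a is negative, so the printed minus root gives RR > 1; the plus root is needed. The divisor 2 inside the squared z term does not follow from the algebra below. It may be an artefact of reading the PDF. Both are corrected from here on, so nothing below depends on them.

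**Step 2: where equation 2 comes from.** Let d = RR − 1, p1 = RR·P/(1+dP) and z = z_α + z_β, with P playing the role of γ. Use the alternative variance for both z terms:

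N·r·(p1−P)²/(r+1) = z²·[p1(1−p1) + r·P(1−P)].

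Multiply by (1+dP)²/[P(1−P)] and collect terms:

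(r+1) + d(1+2rP) + d²·[rP² − N·r·P(1−P)/(z²(r+1))] = 0.

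These are the Annex's constant, b and a. With the pooled variance throughout, b would be r+2P instead. The power formula attaches the pooled variance (r+1)p_c*(1−p_c*) to z_α. The mismatch is therefore structural.

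**Step 3: one setting in full (N=1000, r=0.1, P=0.20).**
- z² = 7.849; a = 0.004 − 16/(7.849×1.1) = −1.849; b = 1.04.
- d = (−1.04 + √(1.0816 + 4×1.849×1.1))/(2×−1.849) = (−1.04 + 3.036)/(−3.698) = −0.540, so the detectable VE is 54.0%.
- In the power formula at that RR: p1 = 0.1032, p_c* = 0.1912 and the signal term is 0.9230. The null variance is 0.1701 (root 0.4124) and the alternative variance is 0.1085 (root 0.3295).
- z_β = (0.9230 − 1.960×0.4124)/0.3295 = 0.348, so power is 63.6%.
- Solving the power formula for 80% gives VE = 61.4%.
- To detect VE 60% at this r and coverage, equation 2 implies N = 716 and the power formula N = 1060 (ratio 1.48).

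**Step 4: other settings.**

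| N | r | Coverage | VE from corrected eq. 2 | Annex power there | VE with 80% power |
|---|---|---|---|---|---|
| 1000 | 0.1 | 10% | 64.9% | 49.0% | 79.8% |
| 1000 | 0.1 | 30% | 49.0% | 70.2% | 53.2% |
| 1000 | 0.25 | 20% | 43.5% | 72.4% | 46.8% |
| 2000 | 0.05 | 20% | 51.8% | 62.9% | 59.3% |
| 2000 | 0.25 | 20% | 33.0% | 75.1% | 34.7% |
| 1000 | 0.5 | 20% | 39.0% | 76.5% | 40.4% |
| 1000 | 1 | 20% | 38.0% | 79.8% | 38.1% |
| 1000 | 0.1 | 50% | 45.6% | 77.6% | 46.6% |
| 1000 | 0.1 | 60% | 46.1% | 80.4% | 45.9% |
| 1000 | 0.1 | 70% | 48.1% | 83.2% | 46.7% |

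Over r = 0.1, 0.2 and 0.25, N = 1000 and 2000, and coverage 10%, 20% and 30%, power runs from 49.0% to 77.0%. Over the same r and N at coverage 40%, 50% and 60% it runs from 74.4% to 80.8%.

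The ratio of required N (power formula to equation 2), over coverage 10–40% and VE 50–70%, is 1.16–1.87 at r=0.1 and 1.12–1.56 at r=0.25.

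**Step 5: which formula is nearer the truth.** Exact binomial enumeration at N=1000, r=0.1, 20% coverage and VE 54.0% gives 65% (score test), 64% (Wald test on the log OR) and 69% (likelihood ratio), against 63.6% from the power formula. At 10% coverage it gives 52%, 42% and 62%, against 49.0%. Only an unpooled Wald test on the difference in proportions comes near 80% (76% and 75%). The planned VE analysis is based on the OR, so that test is not the relevant one.

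**The case against.** **A reader might infer that equation 2 fails whenever controls outnumber cases.** It does not. At low r the null variance is governed by P(1−P) and the alternative by p1(1−p1), with p1 below P. The second is smaller only while coverage is not too high; at 70% coverage and r=0.1 the order reverses (0.237 against 0.269). Over an assumed grid of 280 settings with r below 1 (coverage 5–70%, r 0.05–0.75, N 500–10,000), 133 lie within 2 points of 80%, 86 are at or below 75% (14 of them below 50%), and 12 exceed 82%. This objection stands and limits the point to the region stated.

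**A reader might infer that the protocol reports a wrong figure.** It reports none. The level, the power and every input above are assumptions, and sizes are deferred to requestor-specific protocols, with updating if assumptions fail. This stands too.

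**The RR is labelled approximate.** So this is an approximation used outside its range, not a false statement. But no range is given, and the region of failure is plausible for this design.

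**Other routes exist.** Case-control ratios may be balanced at analysis, for example by matching, and the Annex lists interval width, power and simulation as alternatives. These reduce reliance on equation 2 but do not correct it. The sample-size inflation in the abstract (commonly 20%, with 50% or 100% also allowed) is meant for covariate adjustment. The N ratio exceeds 1.2 in 11 of 12 settings at r=0.1 and in 9 of 12 at r=0.25.

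**The printed equation has larger faults.** As read, it returns RR = 1.31 at N=2000, r=0.1 and 20% coverage. That is a separate matter. Correcting only the sign and z term would leave the present problem in place.

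**Conclusion.** The point holds in a limited region. With about four or more controls per case and coverage of about 10–30%, the corrected equation 2 is anti-conservative against the Annex's own power formula. At a two-sided 5% level and nominal 80% power, both assumed, the VE it returns typically has about 50–77% power. The gap is negligible at r=1, modest at coverage of about 40–60%, and reversed at about 60–70%. No stated result in the protocol is affected; the risk lies in calculations built on the Annex. This should be fixed, but it does not undermine the design.

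**What to change.** Remove equation 2 with its a and b. Define the minimal detectable VE as 1 − RR, where RR < 1 is the value at which the Annex 1 power formula gives the target z_β, found by a one-dimensional numerical solve; or take it from the Annex simulation. State the level, its sidedness and the target power beside any result. Restate any requestor-specific minimal detectable VE or N that was derived from equation 2.

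The cost is a paragraph of Annex wording and a few lines of code. In the low-coverage, many-controls settings the stated detectable VEs will become less favourable and required N will rise. Replacing the equation also disposes of its printed root sign and z term.
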